9.0 DATA COLLECTION

9.1 The forms to be utilized will be the standard RTOG on study form, completion of treatment and follow-up forms of the glioma studies. A study specific flow sheet for the recording of drug administration, doses, blood levels and tumor levels are to be used. Since this is an ongoing flow sheet, it should be copied and forwarded to RTOG Headquarters according to the specified schedule. The completed form will be forwarded when all of the required entries have been made at the scheduled times and upon termination of the study.

0015938

9.2 Data Submission.

Form	Due
On Study Form Radiotherapy prescription, Calculations, localization film	Within one week of commencement of treatment
Radiotherapy Form Treatment Record Boost film	Within one month of completion of treatment
Follow-up Form Sensitizer flow sheet	Midway through treatment, at completion of treatment, then every 3 months and at death.

9.3 The individual laboratories at the participating institutions measuring blood levels by ultra-violet spectrophotometry of high pressure liquid chromatography will have their laboratories calibrated by a sample specimen or set of specimens to be provided by [name] at the University of California, San Francisco. [name] laboratory will act as a reference laboratory for this study and will review the ability of the individual laboratories to reproduce drug level measurements. The laboratories of affiliate members will be calibrated by the laboratory of the full member with whom they are associated.

9.4 The radiologic physics center will have reviewed the dosimetry of each participant in the study. All neurologic reactions of Grade III or IV will be reviewed by [name], the General Neurological consultant to the project.

9.5 Case histories and copies of neurologic examinations recorded by the local neurologists should be forwarded to RTOG Headquarters to be reviewed by [name] in situations in which patients experience a Grade III or IV peripheral or central nervous system neuropathy.

0015939

10.0 STATISTICAL CONSIDERATIONS

- 10.1 This study is a non-randomized Phase I/II evaluation of the combination of misonidazole and neutron radiation for malignant glioma.
- 10.2 In general, 25 patients will be entered into the protocol although termination or dose modification may occur earlier if undue toxicity occurs or if response is completely beyond the limits expected. The protocol will be open to all members who have approved laboratories for the measurement of misonidazole levels and who have access to neutron treatment facilities.

With this sample size we have a 93% chance of seeing any complication that occurs one time out of ten. Furthermore, we have over a 90% chance of accepting the treatment for further testing if the actual local control rate of the new treatment is 45% at one year and less than 25% chance of further testing if the actual control rate at one year is 25%.

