1.0 INTRODUCTION

1.1 Disease Specific Background

The malignant gliomas are rarely controlled by any treatment and are almost uniformly fatal. Survival following conventional neurosurgical intervention and radiotherapy can be measured in terms of months and reported survival frequencies are in the range of 55-67% at 6 months, 27-39% at 12 months, and 8-20% at 24 months. Relentless local growth of tumor rather than metastases kills the patient.

Considerable effort has been made by investigators in recent years to search for newer avenues of approach, including higher doses of conventional photon radiation, combination of chemotherapy and photon radiation, and high LET radiations.

The RTOG and ECOG have a joint current protocol (RTOG 74-01) which tests standard whole brain radiation using photons to a total dose of 6,000 rad against the same radiation dose with a 1,000 rad boost added, or the addition of chemotherapy using BCNU or methyl CCNU + DTIC. Over 600 patients have been randomized. The study was closed in March, 1979, and preliminary analysis shows no difference among the four treatment randomizations. These preliminary findings are consistent with the early reports of the Brain Tumor Study Group investigation of radiation alone versus radiation plus BCNU.

Inasmuch as there are theoretical biological bases for better responses of the tumors to high LET radiation, pilot studies with fast neutron whole brain radiotherapy were undertaken and some initial observations are available.

Thirty-three patients treated at the University of Washington in Seattle and 35 patients treated at Hammersmith, England, showed excellent tumor control with autopsy data showing better than 90% of the patients with gross tumor replaced by

0015921

coagulation necrosis and only reactive astrocytes in the region. However, diffuse gliosis and demyelination suggested that the RBE for neutrons in the brain may be nearly 4 rather than 3. Dosage was reduced 20% which resulted in no observable brain damage, but patients died of persistent, viable tumor.

A current RTOG protocol (RTOG 76-11) is evaluating the combination of photon radiation to 5000 rad with a neutron boost of 500 rad (approximately equivalent to 1500 photon rad). Although this study is still accruing patients and has yet to mature, a dramatic gain has not been demonstrated in the preliminary results of the first sixty patients.

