There has been no unusual adverse reaction to radiation in terms of either normal-tissue acute reactions, or at this point, with one year of observation, late radiation damage. All of the patients studied in the Phase I trial have had advanced disease and thus tumor control has not been easily assessable. It is a general conclusion that the drug used at the recommended maximum tolerated doses is reasonably safe with only occasional neuropathies more severe than Grade II. Most of these have appeared to be avoidable by adequate

0015924

hydration and careful monitoring of the blood levels and the neurologic condition. It is clear from the responses seen to date that the drug warrants further clinical evaluation in a larger patient population in order to establish whether the recommended doses will indeed be tolerated and whether the radiation fractionation schemes will be acceptable in this type patient with these doses of misonidazole.

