2.0 OBJECTIVES

- 2.1 To lay the basis for a randomized phase III of misonidazole and neutron radiation versus misonidazole and photon radiation.
- 2.2 To determine the tolerance of the unusual radiation fraction scheme proposed in this protocol in terms of acute and late normal tissue reaction and damage.
- 2.3 To establish that the tumor clearance rate, disease-free interval and local tumor control rate are within the expected ranges for malignant gliomas.

0015926

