3.0 SELECTION OF PATIENTS AND ELIGIBILITY CRITERIA

3.1 Eligibility criteria.

- 3.1.1 Histologically confirmed malignant glioma, grade III or IV.
- 3.1.2 Tumor must be supratentorial in location.
- 3.1.3 All patients in this study will be over age 18 but less than age 70.
- 3.1.4 Life expectancy of at least four months.
- 3.1.5 Karnofsky Performance status equal to or greater than 50% (see Appendix I).
- 3.1.6 Patients must have a post-surgical, preradiotherapy CT scan for identification of extent of residual tumor.
- 3.1.7 Signed informed consent indicating awareness of the investigational nature of the study. The consent form must be in keeping with the policies of the institution and the National Cancer Institute (see Appendix II).
- 3.1.8 Functional Class I, II, or III (see Appendix V).
- 3.1.9 Patients must have an acceptable neurologic and metabolic status for ambulatory treatment at the neutron facility.
- 3.2.0 Renal function must be adequate with BUN values equal to or less than 25 and creatinine equal to or less than 1.5.

3.2 Ineligibility criteria.

- 3.2.1 Glioma, grade I and II.
- 3.2.2 Tumor which is infratentorial in origin.
- 3.2.3 Prior radiotherapy to the brain.
- 3.2.4 Any active malignancy in another body site.
- 3.2.5 Performance status less than 50 on the Karnofsky scale; Functional Class IV (see Appendix V).
- 3.2.6 Age less than 18 or over 70.

0015927

- 3.2.7 Prior or concurrent chemotherapy. Pre-existing vincristine neuropathy or other severe drug related neuropathies. Concomitant neuropathies of central nervous system changes which would preclude the evaluation of misonidazole effects.

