8.0 PATIENT ASSESSMENTS

8.1 Patient assessment will include the following:

8.1.1 Study Parameters.

	Pre-Treatment	During Treatment	Each Follow-up
History and Physical (including neurological assessments)	x	x	x
Karnofsky Status	x	a	x
Neurological Functional Classification	x	x	x
CT Scan	x		b
CBC, platelets	x	a	b
Urinalysis	x		
BUN, creatinine, uric acid	x	a	b
Alkaline Phosphatase, LDH, SGOT, bilirubin	x	a	b
Electrolytes	x	a	
Total Protein, Albumin	a	a	
Misonidazole Serum level		a	

- a) If receiving misonidazole (see Appendix V for additional assessments).
- b) If indicated.

0015936

- 8.1.2 Misonidazole Toxicity: The frequency, duration and grade of nausea and vomiting occurring in the patient will be recorded and evaluated.
- 8.1.3 The incidence and degree of peripheral and central neurologic toxicity and ototoxicity will be recorded and evaluated as a function of the number of drug administration, total drug dose, and plasma levels.
- 8.1.4 Mean plasma (4-6 hour) blood levels will be recorded for each drug administration and correlated with the observed frequency and severity of gastrointestinal and neurologic toxicity as well as the drug dose administered in terms of mg/m^2 and mg/kg .
- 8.1.5 Reactions to radiotherapy, both acute and late, will be recorded and included in the complete toxicity evaluation (Appendix IV). Toxicity occurring in any organ will be recorded, as will the location of the organ (within or outside of the radiation treatment volume).
- 8.1.6 Late normal tissue reactions should be recorded at the time of each follow-up according to the scale in Appendix VII.

8.2 Criteria for Tumor Response.

- 8.2.1 All neurological exams and CT scans are graded by comparing the results of the current test with the most recent preceding test. The scale below is to be followed:
- | | | | |
|----|-------------------------------------|----|-----------------------|
| -3 | Marked Deterioration | +3 | Marked Improvement |
| -2 | Definite Deterioration | +2 | Definite Improvement |
| -1 | Suspected Deterioration | +1 | Suspected Improvement |
| 0 | No change since previous evaluation | | |

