- 8.2.2 Response is defined as definite (+2) improvement in at least one of these two parameters: neurological examination and CT scan, provided that the patient is on a stable or decreasing dose of steroids. A concomitant increase in steroid dose will rule out a "response" designation at this point. Suspected (+1) improvement will not designate response.

8.2.3 Conversely, progression is defined as definite (-2) deterioration in at least one of these two parameters: neurological exam and CT scan, provided that the patient has not had his/her dose of steroids decreased since the last course of therapy. A concomitant decrease in steroid dose will rule out a "progression" evaluation at that point. Suspected (-1) deterioration will not designate progression.

8.2.4 Stabilized disease (no change) is defined as stability or suspected (+1 or -1) changes in the test parameters, or improvement in one of the parameters, and deterioration in one parameter.

8.2.5 Follow-up assessments are to be done midway through treatment, upon completion of radiotherapy, then every three months until death. Patients receiving misonidazole are to have assessments done prior to each treatment according to misonidazole study parameters (Appendix VI). Every attempt should be made to obtain an autopsy for confirmation of tumor types and for studying radiation-sensitizer effects on normal brain.

8.3 Measurement of Specific End Points.

8.3.1 Relapse free interval will be measured from the first day of treatment until deterioration is documented as defined in 8.2.

8.3.2 Overall survival will be measured from the first day of radiotherapy until death.

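### The 93% chance of seeing a 1-in-10 complication holds for acute effects in all 25 patients, but overstates what the trial can see of late damage

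*Protocol*

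**What the plan says.** Protocol Section 10.2 sets the size of this single-arm study: "In general, 25 patients will be entered into the protocol". It then gives the safety justification: "With this sample size we have a 93% chance of seeing any complication that occurs one time out of ten". The sentence covers every kind of complication, sets no time window and makes no allowance for death.

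Three other parts of the protocol bear on it:

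- Objective 2.2 is to determine the tolerance of the fractionation scheme "in terms of acute and late normal tissue reaction and damage".
- Section 8.1.6 states: "Late normal tissue reactions should be recorded at the time of each follow-up", using the late-morbidity scale in Appendix VII, which has a brain row. Section 8.2.5 sets assessments midway through treatment, "upon completion of radiotherapy, then every three months until death", and asks for autopsy wherever possible.
- Section 1.1 describes the expected course of the disease after conventional surgery and radiotherapy: "reported survival frequencies are in the range of 55-67% at 6 months, 27-39% at 12 months, and 8-20% at 24 months".

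**The concern.** A detection probability of 1 − (1 − p)^n takes n as the number of patients in whom the complication could appear. For acute reactions that is close to the number entered. For late reactions it is smaller, because on the protocol's own figures most patients die within a year. The 93% is nevertheless offered for complications of every kind, while late damage is named in the tolerance objective.

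Late brain injury is a real hazard here. Section 1.1 reports gliosis and demyelination in earlier neutron-treated patients, followed by a 20% dose reduction. Objective 2.1 is to lay the basis for a phase III trial. A reader who finds no late injury among 25 patients and relies on the 93% would credit the trial with more power to exclude such injury than it has.

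**Working it through.** **Inputs.** n = 25 and complication rate 0.10 (Section 10.2). Survival S of 0.55-0.67 at 6 months, 0.27-0.39 at 12 months and 0.08-0.20 at 24 months (Section 1.1).

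**Step 1: reproduce the stated figure.** P(at least one) = 1 − (1 − 0.10)^25 = 0.928, which rounds to 93%. This uses all 25 patients as the denominator.

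**Step 2: expected number alive.** 25 × S gives 13.75-16.75 at 6 months, 6.75-9.75 at 12 months and 2-5 at 24 months.

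**Step 3: the limiting case, onset only at the time point.** If 10% of the patients alive at that time have the complication, each patient entered contributes a probability of 0.10 × S, and P = 1 − (1 − 0.10 × S)^25.

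| Time | S | P(at least one) |
|---|---|---|
| 6 months | 0.55-0.67 | 76-82% |
| 12 months | 0.27-0.39 | 50-63% |
| 24 months | 0.08-0.20 | 18-40% |

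Using whole numbers of survivors instead (14-17, 7-10 and 2-5) gives 77-83%, 52-65% and 19-41%.

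**Step 4: onset spread over earlier months.** Step 3 counts only patients alive on the day. Follow-up runs every three months until death, so events in patients who die before 12 months can also be seen. Assumptions:

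- survival is exponential within 0-6 and 6-12 months, passing through the Section 1.1 values;
- onset is possible from month a, with constant hazard h = −ln(0.90)/(12 − a), so that the risk by 12 months without death is 10%;
- onset is independent of death, and any event before death is seen.

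The probability per patient entered is q = ∫ from a to 12 of h·exp(−h(t − a))·S(t) dt, and P = 1 − (1 − q)^25.

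| Onset possible from | q | P(at least one) by 12 months |
|---|---|---|
| month 0 | 0.058-0.068 | 78-83% |
| month 3 | 0.048-0.060 | 71-78% |
| month 6 | 0.040-0.052 | 64-74% |
| month 9 | 0.033-0.045 | 56-68% |

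As a approaches 12 the result returns to the 50-63% of Step 3. Every case is below 93%.

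**Step 5: the reading that rescues 93%.** If one in ten means one in ten of the patients entered, with deaths already absorbed in the rate, 93% holds by definition. For damage appearing at one year, that rate corresponds to a risk among survivors of 0.10/0.39 = 26% to 0.10/0.27 = 37%.

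**The case against.** **The arithmetic is correct and the sentence can be read so that it is true.** Both points stand. The number reproduces, and Step 5 shows the per-patient-entered reading is coherent. What that reading does not give is a 93% chance of seeing a late injury that affects one in ten of those who live to be exposed to it. Section 10.2 does not say which quantity is meant.

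**The onset time and the survival inputs are assumptions.** This also stands. The protocol fixes no onset time for late damage; the nearest marker is Section 1.2, which describes earlier misonidazole experience "with one year of observation, late radiation damage". The survival range is historical, and entry requires "Life expectancy of at least four months" among other criteria, so survival here could be better. As a sensitivity check, suppose the 45% one-year control rate in Section 10.2 implied 45% alive at one year. Then 25 × 0.45 is about 11 patients, and 1 − (1 − 0.045)^25 = 68% for onset at 12 months. That is higher than 50-63% but still well short of 93%.

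**Autopsy may reveal brain injury already present at death.** It may, and Section 8.2.5 asks for it. It cannot show damage that had no time to develop.

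**Two stronger inferences are not supported.** A reader might conclude that the trial has an even chance or worse of seeing a 1-in-10 late injury by one year. Only the lowest survival figure combined with onset solely at 12 months gives about 50%; earlier onset gives up to 83%. A reader might also conclude that a proportion out of 25 will be reported and will mislead. The protocol does not say how late toxicity will be summarised, and no rule in Section 10.2 turns on seeing no late events.

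**Conclusion.** The concern holds as an overstatement of scope, not as an error of calculation. The 93% is valid where all 25 patients can be observed, in effect for acute complications. For a late complication with a 10% risk by 12 months in the absence of death, the chance of at least one observed case is about 50-63% with onset only at 12 months and about 56-83% with earlier onset. The shortfall from 93% is therefore roughly 10 to 43 points.

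The range rests on the Section 1.1 survival figures, on independence of late damage and death, and on the assumed onset pattern. Better survival or informative autopsies would narrow the gap. Nothing here shows that the sample size must change; the defect is that Section 10.2 states one figure for two situations.

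**What to change.** In Section 10.2:

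- Limit the 93% to acute complications, and say that it assumes all 25 patients are evaluable.
- Add a sentence for late complications along these lines: given the survival in Section 1.1, and assuming onset independent of death, the chance of seeing at least one case of a complication with a 10% risk by 12 months is about 50-63% if onset is only at 12 months and about 56-83% if onset is spread over earlier months.
- State that late morbidity will be shown with the number at risk at each follow-up and a rate among patients still at risk (for example, with death treated as censoring, or with a landmark denominator), alongside the crude proportion.

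Cumulative incidence with death as a competing event would not serve the last purpose by itself. With complete follow-up to death it equals the crude proportion of 25, so it does not show the risk among those who lived long enough to be exposed.

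The cost is a few lines of text, one extra tabulation from data already collected, and a less favourable stated figure. Sample size and conduct are unchanged.

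### With 25 evaluable patients, no exact single-stage cut-off gives both acceptance probabilities stated in Protocol 10.2; the miss is 2.4 or 3.4 percentage points

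*Protocol*

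**What the plan says.** Protocol 10.1 describes the design: "This study is a non-randomized Phase I/II evaluation". Section 10.2 sets the size: "In general, 25 patients will be entered into the protocol".

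For that size, 10.2 first gives a 93% chance of seeing a complication with a true frequency of one in ten. It then gives two decision probabilities:

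- On the favourable side, "we have over a 90% chance of accepting the treatment for further testing", with the condition "if the actual local control rate of the new treatment is 45% at one year".
- On the unfavourable side, "less than 25% chance of further testing if the actual control rate at one year is 25" per cent.

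The section does not give the number of controlled patients that counts as acceptance, and it does not say whether the probabilities are exact or approximate. Its only wording on stopping early is that "termination or dose modification may occur earlier if undue toxicity occurs or if response is completely beyond the limits expected", with no stage size or boundary.

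**The concern.** In a sample of 25 the number of controlled patients is a whole number, so only a few decision rules are possible, and each has one fixed pair of acceptance probabilities. If none of those pairs satisfies both limits, the text promises a performance that a plain 25-patient rule does not have.

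These two figures are the protocol's only quantitative statement of how likely the treatment is to move on to further testing. Objective 2.1, preparing a randomized phase III trial, does not cite them, but it is the kind of further testing they describe. A reader relying on 10.2 would believe in a lower chance of carrying forward a treatment with 25% control, or a higher chance of carrying forward one with 45% control, than the rule actually used would provide.

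**Working it through.** **Inputs, all from Protocol 10.2.** n = 25; favourable control rate 45%, acceptance to exceed 90%; unfavourable control rate 25%, acceptance to stay below 25%. One-year control is treated as a yes/no outcome known for every patient.

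**Companion figure first.** The chance of at least one complication with true frequency 0.10 is 1 − 0.9^25 = 0.928, which rounds to the stated 93%. With 24 patients it would be 1 − 0.9^24 = 0.920. So the paragraph was calculated for 25, and this part is correct.

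**Exact decision probabilities.** If the treatment is accepted when at least r of n patients are controlled, the acceptance probability at true rate p is

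P(X ≥ r) = Σ (x = r to n) C(n, x) p^x (1 − p)^(n − x).

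For n = 25:

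| Accept if at least | At p = 0.45 (stated: over 90%) | At p = 0.25 (stated: under 25%) | Both met? |
|---|---|---|---|
| 7 | 97.4% | 43.9% | no |
| 8 | 93.6% | 27.4% | no |
| 9 | 86.6% | 14.9% | no |
| 10 | 75.8% | 7.1% | no |

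Both columns fall as the cut-off rises. The favourable limit requires a cut-off of 8 or lower, and the unfavourable limit requires 9 or higher, so no single-stage cut-off meets both. The shortfalls are 27.4 − 25 = 2.4 points at 8, and 90 − 86.6 = 3.4 points at 9.

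**Can the stated pair be reproduced another way?**

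1. *Normal approximation, no continuity correction, cut-off 8.* At 25%: mean 25 × 0.25 = 6.25, SD √(25 × 0.25 × 0.75) = 2.165, and 1 − Φ((8 − 6.25)/2.165) = 20.9%. At 45%: mean 11.25, SD √(25 × 0.45 × 0.55) = 2.487, and 1 − Φ((8 − 11.25)/2.487) = 90.4%. Both limits are met. With a continuity correction (7.5 in place of 8) the results are 28.2% and 93.4%, close to the exact values, and the second limit fails again.
2. *One-sample formulas at one-sided alpha 0.25, n = 25.* Power is 92.3% (normal) and 92.5% (arcsine). The normal version places the cut-off at 7.71 patients; in whole patients that is 8 or more, whose exact false-acceptance probability is 27.4%.
3. *Other sample sizes, exact.* 24 patients with at least 8: 91.4% and 23.4%. 27 patients with at least 9: 92.3% and 21.4%. No cut-off works for 26.
4. *Exact two-stage rules totalling 25.* Some work. For example, stop for futility at 4 or fewer controlled of 17, otherwise accept at 8 or more of 25: 91.1% and 24.3%.

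**The case against.** The strongest defence is that the protocol names neither a method nor a cut-off, and that ordinary planning calculations do give both figures. The size is also worded as a general target, and early termination is foreseen, so a fixed sample of exactly 25 is partly the reader's assumption. Finally, the decision rule may be in a statistical analysis plan that is not at hand.

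Parts of this stand. A reader might infer that no rule of any kind in 25 patients can meet both limits. That is not so, because several two-stage rules do. A reader might also infer that the authors must have used one particular approximation. Several routes lead to the stated pair, and the document does not show which was taken. The missing cut-off alone is not the point, since an analysis plan may supply it; nor does the protocol show that anyone intends to choose it after seeing the data.

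The defence does not rescue the text, though. The uncorrected approximation gives 20.9% for a rule whose exact value is 27.4%, so its agreement with the stated limit is approximation error. The 93% in the same paragraph fits 25 patients, not 24. The two-stage rules are not in the protocol: its early-termination wording has no numbers and concerns toxicity or response, and 8.2.2 defines response by improvement on neurological examination or CT, which is a different measure from control at one year.

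**Conclusion.** The point holds in a limited form. For an exact single-stage rule with all 25 patients evaluable, the two probabilities in 10.2 cannot both be true. Either false acceptance at 25% control is 27.4% instead of under 25%, or acceptance at 45% control is 86.6% instead of over 90%.

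The miss is small for a non-randomized phase I/II study with a lenient false-acceptance limit, so this is a low-to-moderate correction. It does not support a stronger reading that the sample size is inadequate or that the design fails: the complication figure is right, and both neighbouring cut-offs come within 3.4 points of the limit they miss.

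The result assumes a binary one-year outcome known for every patient and a single final look. Non-evaluable or censored patients would change it: exactly 24 evaluable patients would happen to satisfy the pair, while 20 to 23 would not under any cut-off.

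**What to change.** In 10.2, state the cut-off for 25 patients and replace the two probabilities with the exact ones for that cut-off. Either of these would do:

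- Accept for further testing if at least 8 of 25 patients are controlled at one year: 94% chance of acceptance if true control is 45%, 27% if it is 25%.
- Accept if at least 9 of 25 are controlled: 87% if true control is 45%, 15% if it is 25%.

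The first keeps the stated power and gives up about 2 points on false acceptance. The second keeps the false-acceptance limit and gives up about 3 points of power. The sponsor should choose and add that the figures are exact binomial probabilities for 25 evaluable patients. If a two-stage rule was intended, its stage size and boundary should be stated instead.

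The cost is one sentence and one slightly less favourable figure, with no change in enrolment. Deciding on only the first 24 patients would match the present text but discard an enrolled patient's outcome. Moving to 27 with a cut-off of 9 would also match it, at the price of two more patients. Neither is needed for a miss of this size.
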